4.1. Primary objectives

- 1) To assess the feasibility of uptake amongst people with 'high risk' or 'very high risk' type 2 diabetes.
- 2) To assess the usability of Fresh Start amongst people with 'high risk' or 'very high risk' type 2 diabetes.
- 3) To assess the acceptability of Fresh Start amongst people with 'high risk' or 'very high risk' type 2 diabetes.
- 4) To assess the acceptability of Fresh Start amongst HCPs.
- 5) To assess the cost-effectiveness of delivering Fresh Start.

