5.2.2. Matched Control Group

Several of the study's objectives and associated outcome measures will require a control group for comparison. This includes the primary objective investigating cost-effectiveness and secondary objectives investigating safety and efficacy of Fresh Start on clinical outcomes.

To achieve this, the study will establish a matched control group using propensity score matching (PSM). PSM uses statistical techniques to construct an artificial control group by matching each study participant with a non-treated participant of similar characteristics. This is achieved by estimating the probability that a person would enrol in a program given a set of pre-defined characteristics, with the resulting probability providing a 'propensity score'.

Data for the matched control group will be identified using NWL's Whole of Systems Integrated Care (WSIC) database. WSIC links provider data from four acute, two mental health and two community Trusts across eight CCGs, social care data from eight boroughs and 380 GP practices to generate an integrated care record.

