5.5. Sample Size

The study will seek to collect and analyse data from a minimum of 300 participants to Fresh Start. With an estimated enrolment rate of 20%, 1,500 eligible patients will need to be identified and we will be able to estimate this rate within a 95% confidence interval of +/-3%, accounting for variance inflation due to clustering with the assumption of 10 GP practices and Intraclass Correlation Coefficient (ICC) of 0.05.

The study's secondary objectives are exploratory only and will not be demonstrated to a level of statistical significance in this study.

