7.1.2. Propensity Score Matching

For the primary cost-benefit comparison and secondary safety and efficacy comparisons, study data will be compared against a matched-control group established via propensity score matching. This is achieved by deriving a propensity score for each enrolled patient based on the following characteristics:

- Age
- Gender
- Geographical proximity
- Social deprivation index (by practice)

- Ethnicity

Using the above categories, taking 'arm' as the dependent variable, logistic regression using a generalised logit model will be used to generate the estimated propensity scores. Scores are also applied to a control 'arm' taken from the WSIC database as section 5.2.2 with everyone in the matched control identified within one month of the index case. The scores are then used to 'pair-up' patients within both groups, patients will be matched on a 1:1 basis without replacement.

Scores are to be calculated using PSOCORE in STATA. Matching is to be carried out using PSMATCH2 (or a suitable alternative). Balancing on matching variables is to be checked once matching is completed using PSTEST. If any variable is found to be unbalanced the matching is repeated, either adjusting the matching method or caliper used.

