7.2. Summary of Analysis Methods

Primary Objective	Outcome	Comp. w/ control?	Analysis Methods
1) To assess the feasibility of uptake amongst people with 'high risk' or 'very high risk' type 2 diabetes .	offered Fresh Start vs. enrolled	No	Frequency and percentage enrolled presented
	enrolled vs. downloading app	No	Frequency and percentage downloading presented
2) To assess the usability of Fresh Start amongst people with 'high risk' or 'very high risk' type 2 diabetes .	VGCs attended	No	Summary stats of VGCs attended overall and per unit time
	emails metrics as section 7.5.2	No	Frequency and percentages presented
	blood glucose measurements recorded	No	Summary stats of meas. recorded by patient overall and per unit time
	blood pressure measurements recorded	No	Summary stats of meas. recorded by patient overall and per unit time
	weight* measurements recorded	No	Summary stats of meas. recorded by patient overall and per unit time
	Diabetes Distress Scale measurements recorded	No	Summary stats of meas. recorded by patient overall and per unit time
4) To assess the acceptability of Fresh Start amongst people with 'high risk' or 'very high risk' type 2 diabetes .	Interviews with patients (x10)	No	As per ICHP team
5) To assess the acceptability of Fresh Start amongst HCPs .	Interviews with healthcare professionals (HCPs, x10)	No	As per ICHP team
6) To assess the cost-effectiveness of delivering Fresh Start.	primary care appointments per patient (as recorded)	Yes	Summary stats of no appts. attended per patient up to 6 months post enrollment

Primary Objective	Outcome	Comp. w/ control?	Analysis Methods
			Comparison between groups via poisson mixed model
	Cost per appointment per patient	Yes	Summary stats of appt. cost per patient. Comparison between groups via mixed model
	Cost of equipment per patient	No	Summary stats of overall cost per patient.

Secondary Objective	Outcome	Comp. w/ control?	Analysis Methods
1) To assess the safety of Fresh Start.	Number of deaths	Yes	Frequency and percentages presented up to 6 months post enrollment
	Number of emergency department admissions	Yes	Frequency and percentages presented up to 6 months post enrollment
	Number of hospital admissions	Yes	Frequency and percentages presented up to 6 months post enrollment. Difference presented with 95% CI
2) To assess the impact of Fresh Start on clinical outcomes .	HbA1c	Yes	Summary stats of HbA1c by visit (BL, W12, M6) Comparison within & between groups via mixed model

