7.5.5. Cost-effectiveness of delivering Fresh Start

From the three sets of data established in 6.2.6, cost-effectiveness of Fresh Start is to be assessed via the following:

- Number of primary care appointments per patient - as entered in study dataset over the 12-week assessment period

Summary statistics will be derived for mean, sd, median, 1st/3rd quartiles, and minimum/maximum. Results will be presented as mean (SD) for normally distributed data and median [Q1-Q3] for skewed.

To assess for differences in frequency of appointments per patient between Fresh Start and the matched control group, a Poisson-based mixed effects model with covariates for sex, age, social deprivation index will be used allowing for clustering by GP practice.

- Cost per appointment per patient - as entered in study dataset

Summary statistics will be derived for mean, sd, median, 1st/3rd quartiles, and minimum/maximum. Results will be presented as mean (SD) for normally distributed data and median [Q1-Q3] for skewed.

To assess for differences in cost of appointments per patient between Fresh Start and the matched control group, a mixed-model approach with covariates for sex, age, social deprivation index will be used allowing for clustering by GP practice.

- Cost of equipment per patient

Imperial Clinical Trials Unit	SUB-STUDY SAP TEMPLATE – SUB-ANALYSES AND OBSERVATIONAL STUDIES	SOP_TEM_BS002
-------------------------------	---	---------------

Costs per patient will be estimated using the figures provided in section 6.2.6.1. Once established, summary statistics will be derived for mean, sd, median, 1st/3rd quartiles, and minimum/maximum. Results will be presented as mean (SD) for normally distributed data and median [Q1-Q3] for skewed

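### The Poisson mixed model for appointments per patient has no term for between-patient overdispersion, so its 95% CI is likely to be miscalibrated, in a direction that depends on where the controls come from

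*SAP*

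**What the plan says.** SAP 4.1 lists among the primary objectives "To assess the cost-effectiveness of delivering Fresh Start". One of its three outcomes is the number of primary care appointments per patient, compared with the propensity-matched controls. SAP 7.5.5 analyses that count with "a Poisson-based mixed effects model with covariates for sex, age, social deprivation index will be used allowing for clustering by GP practice". The table in SAP 7.2 repeats the choice: "Comparison between groups via poisson mixed model". Cost per appointment is a separate outcome with its own model: "To assess for differences in cost of appointments per patient between Fresh Start and the matched control group, a mixed-model approach".

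The planned size is given by "The study will seek to collect and analyse data from a minimum of 300 participants to Fresh Start", and SAP 7.1.2 adds that "patients will be matched on a 1:1 basis without replacement", so about 300 per group. Fresh Start patients are planned "with the assumption of 10 GP practices and Intraclass Correlation Coefficient (ICC) of 0.05"; that ICC belongs to the enrolment rate, not to appointments. Controls come from WSIC, which holds "social care data from eight boroughs and 380 GP practices to generate an integrated care record". Neither document says whether controls may belong to the Fresh Start practices.

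The count window differs within the SAP: 12 weeks in 6.2.5 and 7.5.5, and up to 6 months in 7.2. Neither document mentions overdispersion, a dispersion check, a negative binomial model, a patient-level random effect or robust standard errors.

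**The concern.** A Poisson model with a practice intercept sets the variance of a patient's count equal to its mean, given practice, sex, age and deprivation. Patients in this study will probably differ by more than that. Eligibility runs from two risk factors to established ASCVD. The protocol (3.5 and 3.11) matches on risk category, but the SAP's matching list (7.1.2) omits it and the model does not adjust for it. A likely driver of attendance is therefore left in the residual.

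The standard error matters because it will be reported. SAP Appendix 1 assigns the appointment comparison to Template 5, which is model output with a p-value and a 95% CI. If the SE is too small, a chance difference can look like a real saving or burden. If it is too large, a real difference can be missed. The statement that results are exploratory applies to the secondary objectives (SAP 4.2 and 5.5), and this comparison serves a primary one.

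**Working it through.** **Plan's own figure.** There is none to reproduce: the documents give no mean, SD, dispersion, power or precision for appointments. The means, k values and practice SDs below are assumptions. The 300 per group and the 10 Fresh Start practices come from the SAP.

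**Controls in the same practices.** Take Var = μ(1 + kμ). Group then varies within practice, so the practice effect largely cancels.

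- True SE ÷ Poisson SE = √(1 + kμ).
- Coverage of a nominal 95% CI = 2Φ(1.96 ÷ ratio) − 1.

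| Mean μ | k | SE ratio | Coverage |
|---|---|---|---|
| 2 | 0.1 | √1.2 = 1.10 | 93% |
| 3 | 0.1 | √1.3 = 1.14 | 91% |
| 3 | 0.25 | √1.75 = 1.32 | 86% |
| 3 | 0.5 | √2.5 = 1.58 | 78% |
| 6 | 0.5 | √4 = 2.00 | 67% |
| 3 | 1 | √4 = 2.00 | 67% |

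At mean 3 and k 0.5, the Poisson SE of the log rate ratio is √(2 ÷ 900) = 0.047, a CI factor of ×/÷1.10. The correct SE is √(5 ÷ 900) = 0.075, a factor of ×/÷1.16.

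**Controls in other practices.** Group is now a between-practice contrast, and the estimated practice variance takes up patient-level variation. For a practice with m patients, the excess is about k ÷ m on the log scale, so it is large when controls are thinly spread. The model then applies that inflated variance to the 10 Fresh Start practices as well.

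Example with 100 control practices (3 controls each), mean 3, k 0.5 and true practice SD 0.1. In simulation the mean estimated practice SD was 0.368.

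- Model SE ≈ √(0.368²/10 + 0.368²/100 + 2/900) = √0.0171 = 0.131.
- True SE ≈ √(0.01/10 + 0.01/100 + 5/900) = √0.0067 = 0.082.
- Ratio ≈ 0.62, so the CI is too wide.

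**Simulation of the planned model.** Negative binomial counts, 300 vs 300, were fitted by a Poisson mixed model with a practice intercept only, about 300 runs per setting. Practice SD was 0.1 or 0.2, and (mean, k) was (3, 0.25), (3, 0.5), (6, 0.5) or (3, 1).

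| Where controls sit | True ÷ model SE | Coverage |
|---|---|---|
| Same 10 practices | 1.31–1.97 | 68–86% |
| 30 other practices | 0.87–1.02 | 94–97% |
| 100 other practices | 0.56–0.81 | 98–99.7% |
| 300 other practices | 0.35–0.55 | 97–100% |

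With k = 0 the ratio was 0.97–1.08 and coverage 93–95%, so the model behaves when counts are Poisson. For 300 practices, the larger practice SD was completed only at k of 0 and 0.25.

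**The alternative model.** 120 runs, mean 3, k 0.5, practice SD 0.15:

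| Where controls sit | Poisson: ratio, coverage | Negative binomial: ratio, coverage |
|---|---|---|
| Same 10 practices | 1.57, 79% | 0.99, 94% |
| 30 other practices | 0.94, 96% | 1.03, 95% |
| 100 other practices | 0.69, 98% | 1.00, 94% |

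A separate run of the same-practice layout gave a ratio of about 1.5, with coverage of 84% for Poisson and 94% for negative binomial. With 120 runs, the Monte Carlo error on 95% coverage is √(0.95 × 0.05 ÷ 120) = 2 percentage points.

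**Count window.** At fixed k, a longer window raises μ and so the excess variance. Doubling the mean from 3 to 6 at k 0.5 moves the same-practice SE ratio from 1.58 to 2.00.

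**The case against.** A reader might infer that the CI must be far too narrow because a practice effect cannot absorb patient-level variation. The documents do not support that. WSIC spans 380 practices, and matching uses proximity and a practice-level deprivation index, which suggests that matching can cross practices. With controls in other practices, the planned model gave intervals that were about right or too wide.

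The size is also uncertain. The documents give no dispersion figure, and mild dispersion does little harm. Fresh Start patients follow a fixed schedule of onboarding, three group sessions and a 12-week review. If these contacts count as appointments, which is not stated, they add a near-constant part that lowers the variance relative to the mean in that arm.

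The stakes are limited too. This is a feasibility study, and SAP 7.1.1 describes the primary analyses as descriptive. No threshold or decision rule hangs on this comparison, and the SD and quartiles will be shown beside it.

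All of this stands as a limit on direction, size and consequence. It does not rescue the model. A Poisson interval that is right only when controls happen to be spread in one particular way is not a sound specification. SAP 7.5.5 does plan a between-group model, so the descriptive label does not remove the issue.

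**Conclusion.** The concern holds in a conditional form. The Poisson mixed model has no term for between-patient overdispersion, and its 95% CI for appointments per patient is likely to be miscalibrated. Under the assumed means of 3–6 and k of 0.25–1, simulated coverage is about 68–86% if controls share the Fresh Start practices, about nominal with some 30 other practices, and above nominal, with over-wide intervals, when controls are scattered over 100 or more. At k 0.1 and mean 2–3 with shared practices, the true SE is only 10–14% above the Poisson SE.

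Confidence is high that the provision is missing and low on the size and direction of the error, since both rest on values and a control layout that the documents do not give. A reader might also take this as a flaw in the cost comparison. It is not: the Poisson model applies to appointment numbers, and cost has its own model. The point is worth correcting before analysis, but it does not undermine the study.

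**What to change.** In SAP 7.5.5 and 7.2, replace the Poisson model with a negative binomial mixed model that has a practice random intercept, the same covariates and an offset for each patient's observed time. It reduces to Poisson when there is no overdispersion, and it was calibrated in all three control layouts tested. Report the variance-to-mean ratio by arm beside it.

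State whether controls may come from the Fresh Start practices. Reconcile the 12-week window in 6.2.5 and 7.5.5 with the 6-month window in 7.2.

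Poisson with unclustered robust standard errors is not an adequate substitute, because it ignores practice. Practice-clustered errors would need a small-sample correction with about 10 Fresh Start practices.

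The model change costs one line of SAP text and a different command; the two clarifications take a sentence each. The CI may become wider or narrower than the Poisson one.

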4.5 Withdrawal criteria

Subjects may be withdrawn from the study at the discretion of the investigator team due to a safety concern or if judged non-compliant with trial procedures. Reasons for withdrawals and discontinuation of any subject from the protocol will be recorded by the investigator team.

A subject must be withdrawn from treatment if one of the following applies:

- Subject chooses to withdraw from the study (at any time)
- Major violation of the study protocol
- Other circumstances that would endanger the health of the subject if he/she were to continue his/her participation in the trial

5. Adverse events

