6.1. Summary of Analysis Variables

Primary Objective	Outcome	Source	Freq.	Comp. w/ control?
1) To assess the feasibility of uptake amongst people with 'high risk' or 'very high risk' type 2 diabetes .	Patients offered Fresh Start vs. enrolled	EPR	Once	No
	Patients enrolled vs. downloading Huma app	Huma	Once	No
2) To assess the usability of Fresh Start amongst people with 'high risk' or 'very high risk' type 2 diabetes .	Number of VGCS attended	EPR	Every 4 weeks	No
	Number of Fresh Start emails opened	KD	Twice weekly	No
	Number of blood glucose measurements recorded	Huma	Daily	No
	Number of blood pressure measurements recorded	Huma	Daily	No
	Number of weight* measurements recorded	Huma	Daily	No
	Number of Diabetes Distress Scale measurements recorded	Huma	Monthly	No
3) To assess the acceptability of Fresh Start amongst people with 'high risk' or 'very high risk' type 2 diabetes .	Interviews with patients (x10)	Interview	At 12 weeks	No
4) To assess the acceptability of Fresh Start amongst HCPs .	Interviews with healthcare professionals (HCPs, x10)	Interview	After intervention	No
5) To assess the cost-effectiveness of delivering Fresh Start.	Number of primary care appointments per patient	EPR	Data extracted from EPR	Yes
	Cost per appointment per patient	EPR	Data extracted from EPR	Yes
	Cost of equipment per patient	Huma	N/A	No

* In the event where BMI data is more routinely collected the endpoint may be adjusted to BMI

Secondary Objective	Outcome	Source	Freq.	Compare with control?
1) To assess the safety of Fresh Start.	Number of deaths	EPR	Data extracted from EPR	Yes
	Number of emergency department admissions	WSIC	Data extracted from WSIC	Yes
	Number of hospital admissions	WSIC	Data extracted from WSIC	Yes
2) To assess the impact of Fresh Start on clinical outcomes .	HbA1c	EPR	Baseline, 12 weeks, 6 months	Yes
	Lipids, incl. LDL and non-HDL cholesterol	EPR	Baseline, 12 weeks, 6 months	Yes
	Weight *	EPR	Baseline, 12 weeks, 6 months	Yes
	Diabetes Distress Scale score (DDS[iii])	Huma	Monthly during service (and at 6 month follow-up appt.)	No
	Blood glucose time-in-range	Huma	Daily	Yes
	Systolic blood pressure (SBP)	Huma	Daily	Yes

* Note, if patient Height is also recorded BMI may be presented as an alternative

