7.6. Secondary Analysis Methodology

7.6.1. Safety of Fresh Start

From the safety parameters established in 6.3.1, safety of Fresh Start is to be assessed via the following over 6 months:

- Number of deaths

Number of deaths is to be presented by frequency per group.

- Number of emergency department admissions

Number of patients with emergency admissions is to be presented by frequency per group

- Number of hospital admissions

Frequency of events per patient is to be presented in a frequency table by treatment group with percentages to 1 dp.

Number of patients with hospital admissions is to be presented by frequency per group

Statistical comparison of safety will consist of a composite outcome, including all three events listed above. Number of patients with a safety event occurring is to be presented by frequency per group with difference in number of patients presented with a 95% CI.

7.6.2. Impact of Fresh Start on clinical outcomes.

From the clinical outcome parameters established in 6.3.2, potential efficacy of Fresh Start is to be assessed via the following

- **HbA1c, at baseline, 12-week and at 6 months**
- **Lipids, at baseline, 12-week and at 6 months**
- **Weight, at baseline, 12-week and at 6 months**

Tables displaying summary statistics will be produced displaying mean, SD, median, minimum & maximum at timepoints BL, W12 & M6

Within-group change from baseline at 12 weeks will be assessed via a mixed-effects model taking values at 12-weeks as the dependant variable and adjusting for covariates; baseline, sex, age, social deprivation index and allowing for clustering by GP Practice

Between-group differences in change from baseline at 12 weeks will be analysed using a similar mixed-effects model including an additional parameter for treatment effect and again adjusting for covariates; baseline, sex, age, social deprivation index and allowing for clustering by GP Practice

Further analysis will take place once long-term (6-month) follow-up is completed using an adjusted version of the above models containing additional terms for visit and visit*treatment interaction.

- **Diabetes Distress Scale score (DDS), as recorded within HUMA once monthly across the 12-week assessment period and also at 6 months**

Summary statistics displaying mean, SD, median, minimum & maximum DDS will be produced at for first reading and last reading.

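### The Poisson model for appointments per patient has no exposure term, so unequal observation time between the arms can bias the rate ratio, in either direction

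*SAP*

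**What the plan says.** Cost-effectiveness is a primary objective in both documents, and SAP 7.1.2 sets out the comparison: "For the primary cost-benefit comparison and secondary safety and efficacy comparisons, study data will be compared against a matched-control group". The appointment count comes from routine records in both arms; the SAP 6.1 row reads "Number of primary care appointments per patient EPR Data extracted from EPR Yes".

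The model in SAP 7.5.5 is "a Poisson-based mixed effects model with covariates for sex, age, social deprivation index will be used allowing for clustering by GP practice". The SAP 7.2 table says only "Comparison between groups via poisson mixed model". Neither place names an offset, an exposure variable or person-time.

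The counting window is stated in two ways. SAP 7.5.5 has "Number of primary care appointments per patient - as entered in study dataset over the 12-week assessment period", and SAP 6.2.5 agrees. SAP 7.2 has "Summary stats of no appts. attended per patient up to 6 months post enrollment".

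On incomplete observation, Protocol 4.5 lists "Subject chooses to withdraw from the study (at any time" among the grounds for withdrawal. SAP section 8 allows control patients with missing data to be replaced and gives no corresponding rule for Fresh Start patients. SAP 7.1.2 has controls identified within a month of the index case but does not say on which date a control's count begins. Neither document says whether record extraction stops when a participant withdraws.

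**The concern.** A Poisson model without an offset treats every count as covering the same length of time. If a record ends early through deregistration, withdrawal of permission to use data or an early data cut, the missing weeks enter as weeks without appointments. The fitted ratio then mixes the appointment rate with the length of observation.

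This matters when the two arms lose different amounts of time, and the plan does not ensure that they lose the same. Enrolled patients can withdraw, or be withdrawn for non-compliance; controls are flagged database records with no service to leave. Incomplete controls may be replaced by others, while incomplete Fresh Start patients stay in. Both features make a greater loss in Fresh Start plausible. At stake is whether a ratio below 1 on a primary objective reflects fewer appointments or fewer weeks of record.

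**Working it through.** **The plan's own figure.** There is none to reproduce. The documents give no rate ratio, appointment rate, power or loss rate for this comparison. The only sizing figure carried over is the minimum of 300 Fresh Start participants with 1:1 matching.

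**Formula.** Let wF and wC be the shares of Fresh Start and control patients with a shortened record, and f the mean fraction of the window observed in those patients. If loss is unrelated to the appointment rate, the model without an offset estimates

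apparent RR = true RR × [1 − wF(1 − f)] / [1 − wC(1 − f)].

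**Results with true RR = 1.00.** All loss rates and values of f are assumptions.

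| Fresh Start loss | Control loss | f | Calculation | Apparent RR |
|---|---|---|---|---|
| 10% | 0% | 0.5 | 1 − 0.10 × 0.5 | 0.95 |
| 20% | 0% | 0.5 | 1 − 0.20 × 0.5 | 0.90 |
| 30% | 0% | 0.5 | 1 − 0.30 × 0.5 | 0.85 |
| 20% | 5% | 0.5 | 0.90 / 0.975 | 0.92 |
| 20% | 20% | 0.5 | 0.90 / 0.90 | 1.00 |
| 5% | 10% | 0.5 | 0.975 / 0.95 | 1.03 |
| 0% | 10% | 0.5 | 1 / 0.95 | 1.05 |
| 20% | 0% | 0.25 | 1 − 0.20 × 0.75 | 0.85 |
| 0% | 10% | 0.25 | 1 / 0.925 | 1.08 |

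The distortion is multiplicative. An illustrative true RR of 0.80 would appear as 0.80 × 0.95 = 0.76 in the first row and 0.80 × 0.90 = 0.72 in the second.

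**Simulation check.** The setting was 300 patients per arm, 10 practices, a mean of 3 appointments per window (assumed), true RR 1.00 and 400 runs per scenario. Shortened records ended at times uniform on 0.02 to 1 of the window. A Poisson regression with fixed practice effects stood in for the mixed model.

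| Loss, Fresh Start / control | RR without offset | RR with log(time) offset |
|---|---|---|
| 10% / 0% | 0.948 | 0.997 |
| 20% / 0% | 0.901 | 1.001 |
| 20% / 20% | 1.002 | 1.002 |
| 5% / 10% | 1.028 | 1.002 |

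The offset removes the distortion when loss is unrelated to the appointment rate. If everyone is observed for the whole window, log(days) is a constant and the rate ratio does not change.

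**Deaths.** SAP 7.6.1 says "Number of deaths is to be presented by frequency per group" and gives no expected rate. If time after death were treated as lost, with f = 0.5 and assumed deaths of 2% against 1%, the ratio would be 0.99 / 0.995 = 0.995, or 1.005 the other way round. Deaths at that level hardly move the result.

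**The case against.** A reader might infer that the omission biases the comparison in favour of Fresh Start, so that a service patients abandon would appear to save appointments. The documents do not support that as a finding, for these reasons.

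- Appointments are routine GP records. Leaving the service does not end the record, and nothing says extraction stops. The withdrawal bullets sit under a sentence about withdrawal from treatment, and SAP 7.7 expects to analyse enrolled patients who did not adhere. If extraction continues, withdrawal shortens nothing.
- No appointments happen after death, so for a per-patient count over a fixed window those zeros are real. An offset that stops at death changes the question to a rate while alive.
- It is tempting to say that late enrolees are cut off within the nine-month timeline in Protocol 3.10. The bars of that table are not visible in the text reviewed, Protocol 3.9 plans a month-6 appointment, and a common data cut would shorten both members of a matched pair to a similar degree.
- Direction depends on which arm loses more time. Section 8 itself anticipates missing control data.
- The sentence in SAP 7.5.5 does not name the treatment term either, so its silence on an offset is not a decision to exclude one.
- Poor engagement would be visible beside the appointment result, because SAP 7.5.2 reports attendance and app recordings per patient and per unit of time.

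All of this stands against a claim of direction or size. It does not close the gap: the written model is safe only if ascertainment is complete or equal in the two arms, and the plan states neither. The SAP already uses a time denominator for usability, and Appendix 1 assigns the appointment output to a table shell with a per-day row, so a rate is not foreign to the plan.

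**Conclusion.** The point holds as a conditional one. The model has no exposure term, no rule covers partly observed Fresh Start patients, the window is stated as both 12 weeks and up to 6 months, and the comparison serves a primary objective. Unequal observation time can therefore bias the rate ratio. More loss in Fresh Start would push it towards fewer Fresh Start appointments; more loss in controls would push it the other way. The first is plausible, but its direction and size are unknown.

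The illustrative range is 0.85 to 1.05, from 30% loss in Fresh Start only to 10% loss in controls only. It rests on assumed loss rates, half the window observed in lost patients, and loss unrelated to appointment use. With complete extraction or equal loss (the same share lost and the same f in both arms) the bias is nil. Because the offset does nothing when records are complete and corrects unequal, non-informative truncation when they are not, this is more than a request for detail. It is a cheap improvement.

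**What to change.** In SAP 7.5.5, with matching entries in 6.2.5 and 7.2:

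1. Reconcile the 12-week and 6-month windows for the appointment count.
2. Start each matched control's window at a defined index date.
3. Continue record extraction to the end of the window after a patient leaves the service, unless permission to use the data is withdrawn.
4. Add log(days observed) as an offset. Days end at the earliest of window end, deregistration, withdrawal of data permission or data cut, under the same rule in both arms.
5. Do not treat time after death as unobserved in the main per-patient count. Give a rate-while-alive version only as a sensitivity analysis.
6. Report observed time, deaths and withdrawals by arm.

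The cost is one model term and one variable derived from dates, provided the extract holds them. The limits are that the offset assumes a roughly constant appointment rate over the window and does not correct informative loss, for example if patients who leave are those with unusually high or low appointment use. Item 3 limits that problem by keeping the loss small.
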